## ABBREVIATION LIST

Abbreviation	Full Name
ATAAD	Acute Type A Aortic Dissection
TAR+FET	Total Arch Replacement Combined with Frozen Elephant Trunk Implantation
CPB	Cardiopulmonary Bypass
EACTS/STS	European Association for Cardio-Thoracic Surgery/The Society of Thoracic Surgeons
CTA	Computed Tomography Angiography
ICU	Intensive Care Unit
RRT	Renal Replacement Therapy
AKI	Acute Kidney Injury
KDIGO	Kidney Disease Improving Global Outcomes Criteria
ASIA	American Spinal Cord Injury Association
BMI	Body Mass Index
BSA	Body Surface Area
ECG	Electrocardiogram
LCCA	Left Common Carotid Artery
LSCA	Left Subclavian Artery
FAS	Full Analysis Set
PPS	Per Protocol Set
EDC	Electronic Data Capture
CRF	Case Report Form

## PROTOCOL SUMMARY

Study Title	Arch-Clamping Technique under Mild Hypothermia in Treating with Acute Type A Aortic Dissection: Study Protocol for a Multicenter, Three-arm, Open-label, Randomized, Parallel-controlled Trial
Study Objectives	
(1) To evaluate the validity and safety of arch-clamping technique under mild hypothermia for acute type A aortic dissection (ATAAD) using Sun's procedure with bilateral anterograde cerebral perfusion (bACP) as the comparator.
 
(2) To evaluate the validity and safety of arch-clamping technique under mild hypothermia for ATAAD using arch-clamping technique under moderate hypothermia as the comparator.

Study Design	Multicenter, Three-arm, Open-label, Parallel-controlled, Randomized, Superiority Study
Sample Size	This study plans to include 306 participants, divided into three groups of 102 participants each in a 1:1:1 ratio.
Inclusion Criteria	
(1) Computed tomography angiography (CTA) confirmed as ATAAD according to the 2022 ACC/AHA Guideline for the Diagnosis and Management of Aortic Disease;
 
(2) Adult patients (18-70 years) weighing 50-120 kg;
 
(3) Time interval between the onset of symptoms and operation is less than 14 days;
 
(4) Indications for total aortic arch replacement are available;
 
(5) Signed informed consent and availability for follow-up.

Exclusion Criteria	
(1) History of chronic renal failure, hepatocirrhosis, and hepatic insufficiency;
 
(2) Severe gastrointestinal complications of non-aortic dissection, such as mesenteric ischemia, gastrointestinal bleeding, hepatopancreaticobiliary dysfunction, and intestinal obstruction;

	
(3) History of severe cerebral infarction (with cerebral infarction sequels);
 
(4) Preoperative intubation or unconsciousness;
 
(5) Inflammatory aortic diseases, such as Takayasu arteritis and Behçet's disease etc;
 
(6) History of infectious aortic diseases;
 
(7) History of cardiac and aortic surgery;
 
(8) History of malignancy or previous radiotherapy;
 
(9) Pregnant or feeding women, or anyone planning to reproduce during the test period;
 
(10) Without informed consent signature;
 
(11) Participating in any other clinical trial;
 
(12) Having other causes not eligible for operation.

Study Period	June 2025 to June 2027
Study Methods	
The study is a multicenter, three-arm, open-label, randomized, parallel-controlled trial, which plans to enroll 306 participants diagnosed with acute type A aortic dissection (ATAAD) from 7 hospitals in China. All patients receive total arch replacement (TAR) combined with frozen elephant trunk (FET) implantation and are randomized to Group 1 (arch-clamping technique under mild hypothermia), Group 2 (arch-clamping technique under moderate hypothermia) and Group 3 (Sun's procedure using bilateral antegrade cerebral perfusion) in the ratio of 1:1:1. After a 1-year follow-up, the validity and safety of the mild hypothermic arch-clamping technique for ATAAD is evaluated via the incidence of major adverse events including death, renal replacement therapy, stroke, and paraplegia, as well as times of circulatory arrest, cardiopulmonary bypass, and mechanical ventilation, and length of stay.

Outcome Measures	
1. Primary Outcome Measures
 
(1) Major adverse events include death, renal replacement therapy, stroke, and paraplegia
 
2. Secondary Outcome Measures
 
(1) Circulatory arrest time
 
(2) Cardiopulmonary bypass time
 
(3) Mechanical ventilation time
 
(4) Length of ICU stay

-------------------------	---

## BACKGROUND

Acute type A aortic dissection (ATAAD) is a life-threatening cardiovascular disease with increasing death risk of 1-2% per hour after the onset of symptoms and a 48-hour mortality up to 50%. Surgical repair promptly can save patients' lives, but accompanied with high mortality and morbidities. Postoperative complications such as stroke, spinal cord injury and acute renal failure seriously impact the short- and long-term prognosis of the patients.

Total arch replacement (TAR) combined with frozen elephant trunk (FET) implantation is considered as the effective approach to avoid chronic complications and facilitate future endovascular or reintervention, which is progressively used for the treatment of a variety of pathologies involving the aortic arch and descending aorta. The adjunctive techniques of the procedure include moderate hypothermic circulatory arrest (MHCA) to decrease the core temperature and organic metabolism and selective antegrade cerebral perfusion to protect the brain. However, hypothermia prolongs the cooling and rewarming phases and increases systemic inflammatory response exposure significantly; circulatory arrest increases ischemia-reperfusion risk, impairs coagulation mechanisms, and leads to different severities of

organ injury [5,6]. Therefore, reducing or avoiding circulatory arrest and elevating core temperature are key directions for optimizing surgical techniques.

Several observational studies and meta-analyses elaborated that selected antegrade cerebral perfusion reduces the risk of malperfusion and aortic thromboembolism, with lower operative mortality and major complication rates (i.e. strokes and reoperations for bleeding) compared to other arterial cannulation strategies. The EACTS/STS Guidelines for Diagnosing and Treating Acute and Chronic Syndromes of the Aortic Organ recommend that MHCA (26-28°C) deep hypothermic circulatory arrest (20-22°C) for arch surgery in ATAAD [7]. However, using unilateral or bilateral cerebral perfusion remains controversial. Several studies indicate that unilateral and bilateral cerebral perfusion are similar in preventing postoperative neurological dysfunction, while international guidelines recommend using bilateral antegrade cerebral perfusion (bACP) in cases of the prolonged circulatory arrest [7,8]. In 2019, [name] and colleagues from Beijing Anzhen Hospital proposed a novel technical approach for TAR + FET procedure called arch-clamping technique to treat ATAAD. This approach is performed under MHCA (25-28°C), a FET is deployed in the descending aorta and clamped together with the autologous aorta immediately, then distal perfusion was restored via the femoral artery (Figure 1). This approach is easy to manipulate without additional assistive devices, of which the circulatory arrest time is usually limited to about 3 minutes, as well as significantly reducing the CPB duration. The early outcomes showed it was safe and effective in reducing mortality and morbidities. (Table 1) [9,10].

**Figure 1.** A: Conventional TAR + FET procedure; B: Arch-clamping technique.

**Table 1. The early-outcomes between arch-clamping technique and conventional TAR + FET procedure**

[figure not shown]
Variables	Arch-clamping	Conventional TAR	P value
	Technique (n = 39)	+ FET Procedure (n = 40)	
Circulatory arrest time, (min)	4.1 ± 0.6	23 ± 8.8	0.001
Cross Clamp time, (min)	96.9 ± 4.4	127.1 ± 13.3	0.001
CPB time, (min)	158.4 ± 6.8	198.0 ± 12.6	0.001
Postoperative drainage, (ml) *	465 ± 95.5	440.0 ± 100.5	0.260
Intubation time, (h)	13.6 ± 2.2	34.1 ± 14.3	0.001
Red blood cells transfusion, (U)	4.5 ± 1.5	4.1 ± 1.3	0.210
CRRT, n (%)	1 (2.6)	8 (20)	0.029
Stroke, n (%)	1 (2.6)	2 (5)	0.571
Thirty-day death, n (%)	2 (5)	3 (7.5)	1.000

Values are presented as n (%) or mean ± standard deviation. \* Postoperative 12-hour Drainage; *CPB*, Cardiopulmonary bypass; *CRRT*, Continuous renal replacement therapy.

Our team also try to elevate the core temperature of the circulatory arrest over 28°C. We compared the early outcomes of arch-clamping technique under different temperatures. The results demonstrated that the CPB duration and cross-clamp time were significantly reduced in the mild hypothermia group compared to moderate hypothermia group. Meanwhile, the mild hypothermia group has lower mortality and morbidities, especially for the incidences of stroke, spinal cord injury, and continuous renal replacement therapy (Figure 2) [11]. Our previous studies also found that using bACP as a brain protective strategy can significantly reduce the incidence of permanent neurological dysfunction [12,13]. Therefore, we hypothesize that arch-clamping technique combined mild hypothermia and bACP as a surgical bundle can be effective in minimizing the circulatory arrest time and mitigating multi-organ injury due to temperature changes and prolonged CPB duration.

In summary, we designed a multicenter randomized controlled trial to observe the 30-day and 1-year outcomes of patients with ATAAD after operation, seeking to validate the efficacy and safety of arch-clamping technique under mild hyperthermia

using bACP for the treatment of ATAAD.

**Figure 2.** Postoperative outcomes of using the arch-clamp technique in treating with ATAAD at different temperatures. Cardiopulmonary bypass time and cross-clamp time were presented as minutes; Total hospital stay was presented as days; Other variables were presented as n (%). *CRRT*, Continuous renal replacement therapy.

## STUDY OBJECTIVES

- (1) To evaluate the validity and safety of arch-clamping technique under mild hypothermia for ATAAD using Sun's procedure with bACP as the comparator.
- (2) To evaluate the validity and safety of arch-clamping technique under mild hypothermia for ATAAD using arch-clamping technique under moderate hypothermia as the comparator.

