## STUDY DESIGN

### Summary

The study is a multicenter, three-arm, open-label, randomized, parallel-controlled trial, which plans to enroll 306 participants diagnosed with ATAAD from 7 hospitals in China. All patients receive TAR + FET procedure and are randomized to Group 1 (arch-clamping technique under mild hypothermia), Group 2 (arch-clamping technique under moderate hypothermia) and Group 3 (Sun's procedure using bilateral antegrade cerebral perfusion) in the ratio of 1:1:1. After a 1-year follow-up, the validity and safety of the mild hypothermic arch-clamping technique for ATAAD is

evaluated via the incidence of major adverse events including death, renal replacement therapy (RRT), stroke, and paraplegia, as well as times of circulatory arrest, cardiopulmonary bypass, and mechanical ventilation, and length of stay.

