**ECG and Imaging at Discharge / Postoperative Day 30, 6 Months, and 12**

## Months

- (1) ECG: Assess for myocardial ischemia or infarction.
- (2) Echocardiography
  - Measure diameters including the aortic sinus, ascending aorta, arch, descending aorta, brachiocephalic artery, LCCA, and LSCA;
  - Assess cardiac morphology and function: Ventricular sizes and motion abnormality;
  - Assess aortic valve morphology and function: Leaflet prolapse, regurgitation (degree, regurgitant neck, regurgitant area), presence of paravalvular or anastomotic leaks.
- (3) CTA
  - Measure the diameters of the aortic sinus, ascending aorta, arch, descending aorta, abdominal aorta (proximal and distal regions), and Vital abdominal arteries including celiac trunk artery, superior mesenteric artery, and renal arteries;
  - Assess for anastomotic leak, pseudoaneurysm formation, or prosthetic graft stenosis.

## Laboratorial Tests on Postoperative Day 1

- (1) Complete blood count: Hemoglobin, white blood cell count, neutrophil count, neutrophil percentage, C-reactive protein, platelet count;
- (2) Biomarkers of coagulation function: D-dimer, fibrinogen;
- (3) Biomarkers of myocardial injury: Myoglobin, troponin, creatine kinase-MB, creatine kinase, lactate dehydrogenase, B-type natriuretic peptide;
- (4) Biomarkers of liver function: Albumin, alanine aminotransferase, aspartate aminotransferase, total bilirubin, direct bilirubin.
- (5) Biomarkers of renal function: Serum creatinine, creatinine clearance rate, uric acid, cystatin C;
- (6) Arterial blood gas analysis: PaO2, PaCO2, arterial oxygen saturation, arterial

potassium, arterial lactate.

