### Visit 7: Postoperative 12 Months ( $\pm 7$ days)

- (1) Collect symptoms and physical examination findings.
- (2) Collect laboratory tests, including complete blood count, liver and renal function, etc.
- (3) Collect imaging data, including CTA and echocardiography.
- (4) Collect the occurrence of death, RRT, stroke, and paraplegia.

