## **Primary Endpoint Analysis**

Analysis of the primary endpoint will be based on both FAS and PPS.

The primary efficacy endpoint of this study is the incidence of composite events, and a superiority test will be used.

Hypotheses for test ① are as follows:

Null hypothesis:  $T_1 - C \geq 0$

Alternative hypothesis:  $T_1 - C < 0$

Where  $T_1$  is the incidence of composite events in Experimental Group 1, and  $C$  is that in the control group. The difference in composite event rates between the two groups and the 95% confidence interval will be calculated. If the upper limit of the 95% confidence interval is less than 0, superiority is established.

Hypotheses for test ② are as follows:

Null hypothesis:  $T_1 - T_2 \geq 0.05$

Alternative hypothesis:  $T_1 - T_2 < 0.05$

Where  $T_1$  is the incidence of composite events in Experimental Group 1, and  $T_2$  is the incidence in Experimental Group 2. The difference and 95% confidence interval

between the two groups will be calculated. If the upper limit of the 95% confidence interval is less than 0.05, non-inferiority is established.

Testing will follow the fixed sequence of ①→②; if the previous hypothesis test is met, the subsequent comparison will be performed; otherwise, further comparison will be stopped.

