## **Secondary Endpoint Analysis**

Analysis of secondary endpoints will be conducted based on both FAS and PPS.

Statistical analysis methods will follow the general principles described above.

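### Safety is in both objectives, but AEs and SAEs beyond the four composite components are not in the visit schedule, and no by-arm summary of AEs, SAEs or CTA complications is planned

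*Combined protocol and SAP*

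**What the plan says.** **Objectives.** Safety appears in both Study Objectives. The first is "To evaluate the validity and safety of arch-clamping technique under mild hypothermia for ATAAD using Sun's procedure with bACP as the comparator". The second is "To evaluate the validity and safety of arch-clamping technique under mild hypothermia for ATAAD using arch-clamping technique under moderate hypothermia as the comparator".

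**How safety is to be judged.** The Summary under Study Design says validity and safety are "evaluated via the incidence of major adverse events including death, renal replacement therapy (RRT), stroke, and paraplegia". It then adds a set of durations to the same evaluation: "as well as times of circulatory arrest, cardiopulmonary bypass, and mechanical ventilation, and length of stay". Under Primary Endpoint Analysis the same composite is labelled an efficacy measure: "The primary efficacy endpoint of this study is the incidence of composite events, and a superiority test will be used".

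**Event collection.** Visits 3 to 7 each carry the item "Collect the occurrence of death, RRT, stroke, and paraplegia". Visit 2 records surgical details, including transfusion. The Study Flowchart has a row for major adverse events, limited by its footnote to the same four components.

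**Imaging.** CTA at discharge/day 30, 6 months and 12 months is to "Assess for anastomotic leak, pseudoaneurysm formation, or prosthetic graft stenosis".

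**AE rules.** The Adverse Event Reporting Requirements define AEs and SAEs, grade severity by CTCAE version 5.0, require follow-up of every event, and require SAE reports within 24 hours to the institution's management department and the ethics committee. Investigator Training covers AE recording, and Enhancing Subject Compliance asks patients to report their health status after discharge.

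**Analysis.** Statistical Analysis Content covers trial completion, baseline data, the primary endpoint and the secondary endpoints. For the last it says "Statistical analysis methods will follow the general principles described above". Analysis Populations defines only the FAS and the PPS.

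**The concern.** A trial that sets out to evaluate safety needs a route from the recorded harm to a comparison between arms. Here the route stops at reporting: SAEs go to the institution and the ethics committee, AEs are graded and followed, CTA complications are looked for, and no section carries any of them into a result.

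Both arch-clamping arms clamp the stented graft together with the native aorta and restore distal flow through the femoral artery, and Group 1 is also warmer. Harms such as bleeding that needs reoperation, limb or visceral ischaemia, anastomotic leak or pseudoaneurysm lie outside the four components. The plan gives no means of seeing whether they differ between arms.

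The trial is also open-label. When events are not asked about at fixed visits in the same way in every arm, counts can differ through ascertainment alone. If the safety outcomes are chosen only after results by arm are known, the choice itself is open to question.

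**Working it through.** **1. Follow each kind of safety information through the plan.**

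| Information | Defined | In visit list or flowchart | By-arm analysis stated |
|---|---|---|---|
| Death, RRT, stroke, paraplegia | Yes | Visits 3-7 | Yes, as the composite |
| Arrest, bypass and ventilation times, ICU stay | Yes | Yes | Yes, as secondary endpoints |
| Other AEs, with CTCAE grade | Yes | No | No |
| SAEs beyond the four components | Yes | No | No |
| Leak, pseudoaneurysm, graft stenosis on CTA | Yes | Visits 5-7, as imaging | No |
| Postoperative laboratory values | Yes | Visits 3-7 | No |
| Intraoperative transfusion | Yes | Visit 2 | No |
| Reoperation for bleeding | No | No | No |

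The Baseline Data section analyses laboratory and imaging data descriptively at baseline only. The chi-square/Fisher rule under General Principles is generic. Secondary Endpoint Analysis applies the general principles to the secondary endpoints, all four of which are durations.

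**2. Analysis sets.** The FAS excludes subjects who did not receive TAR+FET and subjects with no follow-up records. The PPS also removes experimental-group subjects switched during surgery to the control procedure. Neither is designated for safety. Both can leave out subjects whose operation was started and in whom a harm could occur.

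**3. The plan's sample size, as the basis for precision.** Inputs from Estimation of Total Sample Size: 13% versus 30%, one-sided 0.025, 80% power, 1:1. With the pooled-variance formula and mean rate 0.215:

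- n = [1.96 × √(2 × 0.215 × 0.785) + 0.8416 × √(0.13 × 0.87 + 0.30 × 0.70)]² / 0.17² = 90.5, rounded up to 91, as stated.
- 91 / 0.90 = 101.1, rounded up to 102 per group; 102 × 3 = 306, as stated.

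The stated 84 per group for hypothesis 2 is smaller and does not drive the total. The point depends on none of these figures; they only fix the arm size.

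**4. Imaging with no stated result.** Three scheduled follow-up CTAs × 306 subjects = 918. This is a ceiling, because deaths and dropouts reduce it.

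**5. What by-arm tables could show.** The documents give no AE rates, so the rates here are assumptions. The 95% half-width for a difference between two arms with common rate p is 1.96 × √(2p(1 − p)/n).

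| Assumed rate | n = 102 per arm | n = 91 per arm |
|---|---|---|
| 2% | 3.8 points | 4.1 points |
| 5% | 6.0 points | 6.3 points |
| 10% | 8.2 points | 8.7 points |
| 20% | 11.0 points | 11.6 points |

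The normal approximation is rough at 2%, where about two events per arm are expected. Such tables would describe harms and show large imbalances; they would not establish equivalence.

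**The case against.** The case for the plan is substantial, and it rules out three stronger readings.

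- **That safety rests on the composite alone.** A reader might infer this, but the Summary under Study Design also names the durations, and these are analysed by arm in both the FAS and the PPS. What stands is that they measure process or recovery, so no separate safety endpoint exists.
- **That no visit collects adverse events.** Visits 3-7 collect the four major adverse events, symptoms, examination findings and laboratory tests, and Visits 5-7 add CTA. The listed examination items include limb pulses, skin temperature and bowel sounds. The gap is the missing general AE/SAE item and the missing analysis.
- **That AEs would come to light only spontaneously.** The Special Notes tell investigators to assess fever, laboratory abnormalities, anaemia, fluid collections and other findings and decide which are AEs. Training, follow-up and 24-hour SAE reporting are required. What remains is that none of this is tied to fixed visits.

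The eCRF is also not among the documents, so an AE page may already exist. That would lower the cost of the fix without supplying the analysis.

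Nor do the documents show that arch clamping raises bleeding risk. The Background's mention of reoperation for bleeding summarises outside studies of cannulation strategy. In Table 1, drainage (465 versus 440 ml, P = 0.260) and red-cell transfusion (4.5 versus 4.1 U, P = 0.210) give no evidence of a difference. Bleeding belongs in a safety table because it is a relevant harm, not because a signal has been seen.

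**Conclusion.** The point holds as a gap between the objectives and the planned collection and analysis. AEs and SAEs are defined and reportable, and CTA complications are assessed. But AEs and SAEs beyond the four components are not in the visit schedule, and none of these data has a by-arm summary or a safety population. The safety conclusion rests on the primary efficacy composite plus four durations, and harms outside these would not be compared.

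A reader might go further and infer that the trial could formally declare the technique safe. The documents do not support that: the decision rules under Primary Endpoint Analysis conclude only superiority or non-inferiority on the composite.

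The size of the gap is best put in terms of content: every AE and SAE outside the composite, and up to 918 follow-up CTAs, reach no stated result. The effect on any particular complication cannot be quantified, because the documents give no rates for these events. The conclusion assumes that no unseen document, such as a separate safety analysis plan, fills the gap. The primary tests and the sample size are unaffected. This is a cheap improvement that should be made.

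**What to change.** **Collection.** Add an AE/SAE row to the Study Flowchart and the same item to Visits 2 to 7, so that events are asked about at the same times in every arm.

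**Population.** Define a safety population of all randomised subjects whose operation was started, analysed by randomised arm, with a supporting table by procedure received.

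**Analysis.** After Secondary Endpoint Analysis, add a descriptive safety analysis outside the fixed sequence. For each arm, report the number and percent with:

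- any SAE;
- any AE of CTCAE Grade 3 or higher;
- reoperation for bleeding;
- CTA-detected anastomotic leak, pseudoaneurysm or graft stenosis, with subjects who had a CTA as the denominator.

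Give the Group 1 minus control and Group 1 minus Group 2 risk differences with 95% confidence intervals.

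**Cost.** Protocol and SAP wording, some site time at each visit, possibly one recurring eCRF page, and a few tables. SAE reporting and CTA are already required. Sample size, type I error and the fixed sequence are unchanged, and no clinical rule is altered.
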